Фонд за науку
Републике Србије

Utility of plasma drug level monitoring and *CYP2C19* genotyping in dose personalization of escitalopram therapy

PsyCise_E

Principal Investigator: **Asst. [name] PhD**

Department of Physiology, Faculty of Pharmacy, University of Belgrade, Serbia

Document Date: 12th January 2022

Clinical trial protocol

Test groups:

PsyCise trial is designed to quantify changes in clinical outcomes in participants treated for depression using personalized antidepressant dosing regimen, based on therapeutic drug monitoring (TDM) and CYP2C19 genotyping; as compared to the standard, “one size fits all” dosing. In order to reach this goal, we have defined two test groups based on the TDM findings. Namely, all participants who enter the trial (Visit 0) will begin taking standard escitalopram dose of 10 mg/day for two weeks when their blood samples will be taken for the purpose of TDM, and based on their steady state escitalopram concentrations they will be allocated to one of two groups at week 4 of the trial (visit 1):

- 1) “Standard dose” group: Participants will be allocated to this group if their TDM results at week 2 show their steady state escitalopram plasma concentrations were inside “therapeutic window” (25-50 ng/ml). For these participants, initial standard escitalopram dose of 10 mg/day is estimated to be optimal so they will continue to receive the same dose until the end of the trial at week 8 (visit 2).
- 2) “Adjusted dose” group: If TDM results at week 2 suggest that participant taking standard dose is underdosed or overdosed, given participant is allocated to this group. New, personalized dosing regimen will be produced for this participants based on steady state escitalopram plasma concentrations measured at week 2, and they will receive personalized escitalopram dose from week 4 (visit 1) until the end of the trial at week 8 (visit 2).

Course of the trial:

Week 0

Initial Visit (Visit 0 – V0)

- Participant will be enrolled at this point if inclusion criteria are met.
- Escitalopram monotherapy for Major Depressive Disorder in previously untreated patient will be initiated at standard dose of 10 mg/day.
- Outcomes measured:
 1. General and socio-demographic information
 2. Clinical questionnaires
 3. Anthropometric measurements
 4. Cardiological assessment
 5. Serum samples for biochemical analyses
 6. Buffy coat samples for DNA extraction and *CYP2C19* genotyping*

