2. Covariables: Test group (Personalized vs Standard dosing), Age, Sex (Male=0, Female=1), Smoking status (0=Non-smoker, 1=Smoker), Alcohol consumption (0=No, 1=Yes), Coffee consumption (0=No, 1=Yes), Use of psychoactive substances (0=No, 1=Yes), Metabolic syndrome (0=No, 1=Yes), Creatinine clearance, AST/ALT ratio.

Positive outcome: Test group is a significant factor ($\alpha=0.05$)

Secondary outcomes:

Retrospective TDM data on 2087 patients taking escitalopram [Jukić 2018] suggests that, in the clinical setting, about 40% of patients are expected to have their plasma escitalopram concentrations under the lower limit of the therapeutic window (25 ng/ml), and for about 10% of patients we expect to have plasma escitalopram levels above the upper limit of the therapeutic window (50 ng/ml). One of our aims is to try to confirm these findings using prospective study design which allows for the better control of the confounding factors compared to the retrospective data. Number of the patients with plasma escitalopram levels outside the therapeutic window under standard dosing regimen (10 mg/day) will be assessed using TDM data at Mid-Visit (VK), 2 weeks after the beginning of the therapy.

Big disadvantage of TDM guided establishment of the optimal drug exposure in the given patient is that it takes 4 weeks to personalize escitalopram dose and 2 more weeks to achieve optimal steady state drug concentrations. Alternative approach would be to build model that could predict optimal dose for every patient even before the initiation of the treatment. This model would have to include patient data on factors that could impact escitalopram exposure such as body weight, liver and kidney functions and genotype for the *CYP2C19* gene which is responsible for the interindividual variability in the rate of escitalopram metabolism in liver [Jukić 2018]. After all participants have finished the trial we will retrospectively build model using data collected during the trial, and then validate our model comparing it to the TDM method of dose personalization. For this purpose, all patients will be genotyped for *CYP2C19* gene and divided into 4 groups based on the enzymatic capacity of CYP2C19 enzyme:

1. Poor metabolizer (PM): Carries *2/*2, *2/*3 or *3/*3 *CYP2C19* genotype. Almost absent CYP2C19 enzyme activity
2. Intermediate metabolizer (IM): Carries *1/*2 or *1/*3 *CYP2C19* genotype. Reduced CYP2C19 enzyme activity

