3. Normal metabolizer (NM): Carries *1/*1 *CYP2C19* genotype. Normal CYP2C19 enzyme activity
4. Ultra rapid metabolizer: Carries *1/*17 or *17/*17 *CYP2C19* genotype. Increased CYP2C19 enzyme activity

Multiple linear regression model will be build using selected variables:

1. Dependent variable: Plasma escitalopram concentrations at Week 2 (Vk) after the initiation of the treatment
2. Independent variables: Body mass index, PM status (0=Yes, 1=No), IM status (0=Yes, 1=No), NM status (0=Yes, 1=No), UM status (0=Yes, 1=No), Creatinine clearance, AST/ALT ratio

Other outcome measures/observations:

To further validate our primary outcome measures: escitalopram treatment efficacy and severity of adverse effects, we will use Clinical Global Impression (CGI) scales. Scores will be determined for all 3 CGI scales: for Severity of illness (CGI-S) scale at baseline, visit 1 and visit 2, and for Global improvement (CGI-I) scale and for Efficacy Index (CGI-E) at visits 1 and 2. Differences in all 3 CGI scales between visits 1 and 2 will be compared between test groups separately using ANCOVA tests with the equivalent sets of covariates to the ones used for HAM-D scale.

In all patients at baseline and at visits 1 and 2, electrocardiography will be performed in order to monitor potential QT interval prolongation. We will test for correlation between QT interval length and escitalopram plasma levels at various visits, and also we will compare changes in QT interval length between visit 1 and visit 2 in both test groups using mixed ANCOVA test adjusting for the baseline QT length.

Due to high comorbidity of anxiety and depression, and since escitalopram is frequently prescribed in anxiety disorders, we will explore severity of anxiety symptoms in all participants at baseline (V0), Week 4 (V1) and Week 8 (V2) of the treatment by using clinician reported Hamilton anxiety rating scale (HAM-A). Severity of anxiety symptoms will be compared between two test groups at two time points (V1 and V2) using mixed analysis of covariance (Mixed ANCOVA). Variables to be considered as covariates will be: Baseline HAM-A score (V0), Childhood trauma questionnaire score at V0, Age, Sex (Male=0, Female=1), Smoking status (0=Non-smoker, 1=Smoker), Alcohol consumption (0=No, 1=Yes), Metabolic syndrome (0=No, Yes).

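### The only planned QT–concentration test correlates absolute QT with plasma level and leaves out the V0 QT that the trial already records; adding it is a cheap gain for an exploratory safety analysis.

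*Combined protocol and SAP*

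**What the plan says.** The SAP section Other outcome measures/observations says that "electrocardiography will be performed in order to monitor potential QT interval prolongation", in all patients, at baseline and at visits 1 and 2. Two analyses follow in one sentence:

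- **Exposure–response:** "We will test for correlation between QT interval length and escitalopram plasma levels at various visits". No baseline term, change from baseline or covariate is given, and the visits are not named.
- **Group comparison:** QT change from V1 to V2 in the two test groups, "using mixed ANCOVA test adjusting for the baseline QT length". Plasma level does not appear in it.

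Under Course of the trial, ECG and plasma are both scheduled at V1 and V2. In the standard course V0 has an ECG before treatment and no plasma sample, and the week-2 mid-visit has plasma but no cardiological assessment. In the alternative course patients enter already on stable escitalopram, so their V0 ECG and plasma sample are both on drug.

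Under Test groups, patients whose week-2 level lies outside 25–50 ng/ml receive an individual dose from V1 to V2, and the others stay on 10 mg/day.

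**The concern.** Prolongation is a change from a patient's own value. Correlating absolute QT with plasma level asks a different question: whether patients with higher levels have longer QT than other patients. Much of the spread in QT between patients may be there before any drug is given, and in this test that spread counts as noise. The V0 ECG could remove part of it, but the plan does not use it here.

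The design also intends a narrower range of levels at V2 than at V1, and a narrower range weakens a correlation at that visit. No planned analysis describes individual change in QT from V0.

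What is at stake is the safety reading. A null result from an insensitive test says little about drug-related prolongation, and a correlation coefficient, unlike a slope with its interval, does not show what size of effect has been excluded.

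**Working it through.** The documents give no sample size, power or effect size for QT, so there is no figure to reproduce. The steps below illustrate the size of the loss.

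**1. Spread of levels on the standard dose.** Secondary outcomes expects about 40% of patients below 25 ng/ml and about 10% above 50 ng/ml. Assume that these shares apply at 10 mg/day and that levels are lognormal.
- Log-SD = ln(50/25) / (1.2816 + 0.2533) = 0.6931 / 1.5349 = 0.452.
- Median = 25 × exp(0.2533 × 0.452) = 28.0 ng/ml; mean 31.0; SD 14.8.

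**2. What V0 adjustment removes.** Let S be the QT SD between patients, ρ the correlation of V0 with V1 QT, b the slope in ms per ng/ml, and e = b × SD of level.
- Raw QT: r = e / √(S² + e²).
- V0-adjusted: r = e / √(S²(1 − ρ²) + e²).
- N for 80% power, two-sided 0.05 (assumed, since none is stated for QT): N = (2.802 / atanh r)² + 3.

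Example at V1 with b = 0.2 and S = 20 ms (both assumed): e = 0.2 × 14.8 = 2.95.
- Raw: r = 2.95 / √(400 + 8.7) = 0.146, N about 366.
- ρ = 0.6: r = 2.95 / √(256 + 8.7) = 0.181, N about 236. Ratio 366/236 = 1.55.
- ρ = 0.8: r = 2.95 / √(144 + 8.7) = 0.239, N about 135. Ratio 366/135 = 2.7.

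The ratio is close to 1/(1 − ρ²) and hardly depends on b or S:

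| ρ (V0 with V1 QT) | Equivalent multiple of patients |
|---|---|
| 0.3 | about 1.1 |
| 0.5 | about 1.3 |
| 0.6 | about 1.55 |
| 0.7 | about 1.95 |
| 0.8 | about 2.75 |

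Over b = 0.1–0.2, S = 20–25 ms and ρ = 0.6–0.8, r is 0.06–0.15 raw and 0.07–0.24 adjusted. A simple change score is less safe than a covariate: its variance factor is 2(1 − ρ), which gains nothing at ρ = 0.5 and is 1.4 at ρ = 0.3.

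**3. Narrowing at V2.** If every patient ends with the spread that the fitted distribution has inside 25–50 ng/ml, the V2 SD is about 6.7, or 6.7/14.8 = 0.45 of the V1 value. When out-of-window patients are instead simulated as moved into the window with a residual CV of 0–35%, the ratio runs from 0.32 to 0.73. With b = 0.2, S = 20 ms and raw QT, e = 0.2 × 6.7 = 1.34, r = 0.067, and N is about 1,760 at V2 against about 366 at V1.

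**4. Whether the group comparison fills the gap.** From the same shares, the Adjusted-dose group is 40/(40 + 10) = 80% under-exposed (mean about 18.7 ng/ml) and 20% over-exposed (mean about 63.1). If both move to about 35.4, the shifts are +16.7 and −27.7. The net is 0.8 × 16.7 − 0.2 × 27.7 = +7.8 ng/ml. Opposite movements largely cancel in the group mean, so the comparison is a weak substitute for an exposure–response analysis.

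**5. Cost of restricting to a drug-free V0.** The gain is cancelled when the share of patients lost is 1 − 1/ratio: 1 − 1/1.55, about 35%, at ρ = 0.6, and 1 − 1/1.33 = 25% at ρ = 0.5.

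**The case against.** Most of the case on the other side limits the point without removing it.

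- **Tier.** This is an exploratory outcome. None of the four hypotheses concerns QT, and no alpha or success rule is set for it. A reader might infer that the sponsor would present a null correlation as proof of cardiac safety; nothing in the documents says so. This stands.
- **Baseline QT is not overlooked.** The same sentence adjusts the group comparison for it. A reader might infer that the plan ignores baseline QT altogether; it does not. The gap is confined to the correlation.
- **Separate visits are not stated.** A reader might infer a visit-by-visit analysis, but the wording leaves open whether visits are pooled. Pooling in a simple correlation would, however, treat repeated measures on one patient as independent, so the plan needs a statement either way.
- **V1 is intact.** It precedes re-dosing and keeps the full range of levels on the standard dose. The narrowing weakens V2 alone, by an amount that depends on how well re-dosing works, which the trial itself sets out to learn.
- **The numbers are assumed.** QT SD, ρ, slope and sample size are not in the documents, and the 40% and 10% shares come from retrospective clinical data with no dose attached. At b = 0.1 and S = 25 ms, N is about 2,256 raw and still 816–1,446 after adjustment (ρ = 0.8–0.6), so low power may outlast the remedy. This stands.
- **Confounding.** Something that shifts both QT and level could also distort the correlation, but the documents identify no such factor, and V0 QT would remove its effect only in part. The point does not rest on it.

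**Conclusion.** The point holds as a recommended improvement to an exploratory safety analysis. The text establishes three things: the only QT–concentration test uses absolute QT, the V0 value is collected in all patients and not used in that test, and the baseline-adjusted analysis has no concentration term. It follows that a non-zero V0–V1 QT correlation leaves avoidable noise in the test, and that a correlation at V2 alone is less informative than one at V1 if re-dosing works as intended.

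The size is illustrative. The gain is negligible if ρ is near 0.3, moderate at 0.5–0.6 and large at 0.8. The absolute power figures rest further on the assumed slope, QT SD and lognormal levels at 10 mg/day. A reader might infer that the planned correlation cannot detect a QT effect; the documents do not support that, because the sample size is not given and a steeper slope would be easier to find. The primary conclusions are untouched.

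**What to change.** Replace the simple correlation in the SAP with a mixed model:

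- **Main model:** QT at V1 and V2 as outcome, plasma level at the same visit as exposure, V0 QT as covariate, and a random patient intercept. Report the slope in ms per ng/ml with its 95% CI. Using both visits together avoids reading the narrower V2 range alone, allows for repeated measures, and draws on the within-patient change in level that re-dosing produces.
- **Baseline definition:** treat V0 as a drug-free baseline only for standard-course patients.
- **Parallel model:** the same model without V0 adjustment, including all patients, so that alternative-course patients, whose V0 ECG is on drug, are kept. Report both.
- **Individual changes:** tabulate QT change from drug-free V0 at V1 and V2 by level (<25, 25–50, >50 ng/ml).

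Every ECG and plasma sample is already scheduled, so the change is to SAP wording plus one extra model. The V0-adjusted estimate covers only patients with a pre-treatment ECG. The documents do not say how many will enter by the alternative course; if about 35% do and ρ is 0.6, the gain in precision is cancelled, which is a further reason to report the all-patient model beside it.

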(*Sample is not time dependent, it can be taken at any visit)

Week 2

Mid-Visit (Vk)

- Escitalopram plasma concentrations reach steady state.
- Plasma sample taken for the purpose of TDM and group allocation.

- Percentages of participants who are underdosed and overdosed will be measured and used to confirm previous findings [Jukić 2018]

Week 4

Visit 1 (V1)

- Participants are allocated to the “Standard dose” or “Adjusted dose” group
- Independent clinician prescribes new dosing regimen to the participants in “Adjusted dose” group, and informs patients in “Standard dose” group to continue taking the same standard escitalopram dose.
- Clinician who usually monitors given patient is unaware of the group patient is allocated to, or the dose prescribed to a patient at Visit 1.
- Outcomes measured:
 1. Clinical questionnaires
 2. Anthropometric measurements
 3. Cardiological assessment
 4. Serum samples for biochemical analyses
 5. Plasma samples to reconfirm TDM findings in VK

Week 8

Visit 2 (V2)

- Final visit of the trial and the end of the follow-up.
- Outcomes measured:
 1. Clinical questionnaires
 2. Anthropometric measurements
 3. Cardiological assessment
 4. Serum samples for biochemical analyses
 5. Plasma samples to reconfirm TDM findings in VK and V1 for Standard dosing group, and to determine whether personalized dose is optimal for the patients in Personalized dosing group.

If needed, alternative course will be used:

Week 0

Initial visit + Mid-visit (V0+k)

- Participant on the stable (longer than 2 weeks) monotherapy of Major Depressive Disorder with standard dose of escitalopram (10 mg/day) will be enrolled if other inclusion criteria are met.
- Outcomes measured:
 1. General and socio-demographic information
 2. Clinical questionnaires
 3. Anthropometric measurements
 4. Cardiological assessment
 5. Serum samples for biochemical analyses
 6. Plasma sample for the purpose of TDM and group allocation.
 7. Buffy coat samples for DNA extraction and *CYP2C19* genotyping*

(*Sample is not time dependent, it can be taken at any visit)

Week 2

Visit 1 (V1) – *Identical to the standard protocol*

- Participants are allocated to the “Standard dosing” or “Personalized dosing” group
- Independent clinician prescribes new dosing regimen to the participants in “Personalized dosing” group, and informs patients in “Standard dosing” group to continue taking the same standard escitalopram dose.

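### The ECG analyses name QT interval length with no heart-rate correction or covariate, which adds noise and dilutes any true concentration–QT correlation

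*Combined protocol and SAP*

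**What the plan says.** The ECG analyses are in the Statistical Analysis Plan under "Other outcome measures/observations", so they are neither primary nor secondary. The purpose is given as follows: "electrocardiography will be performed in order to monitor potential QT interval prolongation". ECGs are taken at baseline, visit 1 (V1) and visit 2 (V2).

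Two analyses are planned:

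- **Exposure.** "We will test for correlation between QT interval length and escitalopram plasma levels at various visits". No adjustment is mentioned.
- **Group by visit.** "we will compare changes in QT interval length between visit 1 and visit 2 in both test groups", and this is done "using mixed ANCOVA test adjusting for the baseline QT length". No other covariate is named.

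The visit schedule in the protocol part lists only "Cardiological assessment" at V0, V1 and V2. No ECG method is described. QTc, a correction formula, the RR interval and heart rate are not mentioned anywhere. Nor does the text say that QT is to be left uncorrected.

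The groups are not randomised: "based on their steady state escitalopram concentrations they will be allocated to one of two groups at week 4 of the trial".

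**The concern.** The measured QT interval depends on heart rate as well as on repolarisation. An analysis meant to detect prolongation has to separate the two, either by correcting QT for rate or by modelling rate. The plan names QT length as the outcome in both analyses and as the baseline covariate, and does neither.

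Adjusting for baseline QT does not fill the gap. It accounts for stable differences between patients, but not for a heart rate that differs between V1 and V2. The correlation analysis has no stated adjustment at all.

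These are the plan's only QT analyses, in a trial about exposure-guided dosing. A weak or null concentration–QT result could be taken as reassurance when the outcome was simply too noisy.

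**Working it through.** The plan gives no QT threshold, QT SD, heart-rate figure or sample size for these analyses, so there is no figure of its own to reproduce. All numbers below rest on assumed inputs and show scale only.

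**Formula.** Under the Fridericia (cube-root) correction, QT = QTcF × (60/HR)^(1/3), since RR = 60/HR seconds.

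**1. Dependence on heart rate (assumed QTcF constant at 420 ms).**
- 60 bpm: 420 × (60/60)^(1/3) = 420.0 ms
- 80 bpm: 420 × (60/80)^(1/3) = 381.6 ms
- 72 bpm: 420 × (60/72)^(1/3) = 395.2 ms
- 77 bpm: 420 × (60/77)^(1/3) = 386.5 ms

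A mean shift from 72 to 77 bpm therefore moves QT by 395.2 − 386.5 = 8.7 ms with no change in repolarisation.

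**2. Noise in the V1 to V2 change (assumed mean 72 bpm, within-patient heart-rate SD 5 to 10 bpm, independent between visits).** The slope at 72 bpm is QT/(3 × HR) = 395.2/216 = 1.83 ms per bpm. The SD of the difference between two visits is about √2 × SD(HR) × 1.83.
- SD 5 bpm: 1.414 × 5 × 1.83 = 12.9 ms
- SD 10 bpm: 1.414 × 10 × 1.83 = 25.9 ms

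Simulation, which keeps the curvature, gives 13.1 and 26.9 ms. Hence about 13 to 27 ms.

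**3. Does baseline QT remove it?** In the same simulation with a constant, patient-specific QTc, the V2 − V1 change in QT had essentially no correlation with baseline QT (|r| below 0.003). The named covariate removes none of this noise.

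**4. Effect on the correlation (assumed QTc mean 400 ms, SD 15 to 20 ms; heart rate mean 72 bpm, SD 8 to 12 bpm; true QTc–concentration correlation 0.30).** If heart rate varies independently of concentration, simulation puts the correlation with uncorrected QT between 0.16 (QTc SD 15 ms, heart-rate SD 12 bpm) and 0.24 (20 ms, 8 bpm). It is diluted but does not vanish.

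**5. What bias would require.**
- *Correlation.* If heart rate correlated −0.2 with concentration and concentration had no effect on QTc, uncorrected QT would show a spurious correlation of about 0.12 to 0.17.
- *Masking.* From QTcF 400 ms and 70 bpm, a true 10 ms increase is fully hidden if heart rate rises to 70 × (410/400)^3 = 75.4 bpm.
- *Group comparison.* A shift like those above biases the group-by-visit contrast only by the amount that it differs between groups. A shift common to both groups cancels approximately.

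The documents give no heart-rate data, so nothing in step 5 can be shown to occur in this trial.

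**The case against.** The strongest reply is that the plan never says uncorrected QT. Its wording is generic, and the investigators may intend QTc. That is fair: the absence of correction is inferred from silence. But on that reading the endpoint is left undefined and the formula is open to choice after the data are seen. The choice matters: for a fall from 70 to 65 bpm at a constant QTc of 400 ms, the implied change in measured QT is 9.5 ms under the cube-root formula and 14.0 ms under the square-root (Bazett) formula. The same edit is needed either way.

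A reader might also infer that heart-rate changes will be mistaken for a drug effect, or will conceal one, in the group comparison. The documents do not support that. Such bias needs a different mean heart-rate change in the two groups, and nothing in the plan says that escitalopram or its dose alters heart rate. The groups are formed by plasma level and only one has its dose changed, so equal change cannot be assumed. But the adjusted group pools underdosed and overdosed participants, expected at about 40% and 10% of patients (Secondary outcomes). Their exposure is meant to move in opposite directions, so an exposure-related shift would partly average out. Rate correction does not cure that pooling.

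Finally, this is an other outcome with no stated threshold or positive-outcome criterion. That limits the importance of the point but does not remove it.

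**Conclusion.** The point holds in limited form. Followed literally, the plan analyses a rate-dependent measure, and its one covariate does not correct for rate change after baseline. The expected consequence is loss of precision in both analyses and a diluted concentration–QT correlation. Bias in either analysis is possible but not established.

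The illustrative sizes are an added SD of about 13 to 27 ms in the V1 to V2 change, and a fall in a true correlation of 0.30 to about 0.16–0.24. They depend entirely on the assumed QTc, heart-rate means and SDs. They also assume the cube-root relation, heart rate that varies independently between visits (for the SD) and heart rate that is independent of concentration (for the correlation).

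The HAM-D and UKU conclusions are unaffected. The change is worth making because the named variable is a worse choice than a readily available one.

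**What to change.** In the ECG paragraph under other outcome measures:

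- Replace QT by a prespecified rate-corrected QT, for example QTcF = QT / RR^(1/3) with RR in seconds, in the concentration correlation, the mixed ANCOVA and the baseline covariate.
- Alternatively, keep QT and include RR or heart rate at each visit as a covariate, with the correlation adjusted in the same way.
- Name the formula or model before the data are examined.
- Report uncorrected QT and heart rate descriptively by group and visit, so that any difference in heart-rate change can be seen.

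The cost is SAP wording plus recording heart rate from the same ECG. No extra visit or procedure is needed.

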Alongside with HAM-A scale we will also use serum cortisol levels as a biomarker for anxiety disorders in our population. Cortisol levels will be analyzed in a similar way to HAM-D and HAM-A scores using mixed analysis of covariance (Mixed ANCOVA) with covariates being: Baseline Cortisol serum levels (V0), Childhood trauma questionnaire score at V0, Age, Sex (Male=0, Female=1), Smoking status (0=Non-smoker, 1=Smoker), Alcohol consumption (0=No, 1=Yes), Metabolic syndrome (0=No, Yes). Additionally, correlation between HAM-A score and cortisol levels will be tested.

Since stress, trauma and socio-economic status can all be a part of depressive disorder pathogenesis, we will explore these environmental factors in order to determine their role in the clinical pictures of our participants. Outcome measures used will be:

1. Perceived stress score measured at baseline, visit 1 and visit 2,
2. Childhood trauma score measured at baseline,
3. Employment status (1=Unemployed, 2=Employed; monthly incomes <40 000 RSD, 3=Employed; monthly incomes 40 000-80 000 RSD, 4=Employed; monthly incomes >80 000RSD).
4. Marital status (1=Unmarried, 2=Married, 3=Divorced, 4=Widowed)
5. Education level (1=Primary education (8 years), 2= High school diploma (8+3 or 8+4 years), 3= Associate's degree (8+4+2 or 8+4+3 years) 4= Bachelor's degree (8+4+4 years or higher)

We will separately test for the correlation between these variables and HAM-D score, HAM-A score and CGI-S score.

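### The plan tests correlation with marital status coded 1 to 4, although the variable is nominal, and specifies no method suited to it

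*Combined protocol and SAP*

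**What the plan says.** The relevant text is the last part of the Statistical Analysis Plan, under "Other outcome measures/observations". It lists five environmental variables: perceived stress score, childhood trauma score, employment status with income bands, marital status and education level. The stated aim is that "we will explore these environmental factors in order to determine their role in the clinical pictures of our participants".

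Marital status is given as "Marital status (1=Unmarried, 2=Married, 3=Divorced, 4=Widowed"). One sentence then sets the analysis for the whole list: "We will separately test for the correlation between these variables and HAM-D score, HAM-A score and CGI-S score". It names no coefficient, excepts no variable, and mentions neither indicator variables nor a comparison of groups.

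Two other places are useful for comparison:

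- In the same list, education runs upwards from "Education level (1=Primary education (8 years), 2= High school diploma (8+3 or 8+4 years"), so its codes carry a real order.
- Under Secondary outcomes, the CYP2C19 metabolizer groups enter the regression as separate indicators: "PM status (0=Yes, 1=No), IM status (0=Yes, 1=No), NM status (0=Yes, 1=No), UM status (0=Yes, 1=No"). They are not entered as a single score from 1 to 4.

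**The concern.** Pearson, Spearman and Kendall coefficients all use the order of the codes, and Pearson also uses their spacing. For marital status neither exists: nothing makes Widowed more of anything than Married. A correlation on the codes therefore measures only whether the outcome rises or falls along an arbitrary sequence of labels. Naming a rank method would not cure this.

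The analysis could fail in two ways. If marital groups differ in a pattern that does not follow the sequence 1-2-3-4, the coefficient can be near zero and the difference is missed. If the pattern happens to follow the sequence, a trend is reported that describes no real gradient. This would apply to three scores: HAM-D, HAM-A and CGI-S.

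**Working it through.** The plan states no figure for this analysis, so there is none to reproduce. The check asks whether the answer depends on the labels. Only the codes come from the plan. Group shares, means, SD and sample size below are assumptions.

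**Illustration 1 (population values).** Shares p = 0.35, 0.40, 0.15, 0.10 for Unmarried, Married, Divorced, Widowed; HAM-D means m = 16, 14, 18, 18; within-group SD 6.

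- Overall mean: 0.35×16 + 0.40×14 + 0.15×18 + 0.10×18 = 15.7.
- Between-group variance: 0.35×0.3² + 0.40×1.7² + 0.15×2.3² + 0.10×2.3² = 2.51. Total variance: 36 + 2.51 = 38.51, so the total SD is 6.206.
- Label-free association: eta = √(2.51/38.51) = 0.26, or about 6.5% of variance.

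*Codes as listed (1, 2, 3, 4).*

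- Mean code 2.00; variance 0.35×1 + 0.40×0 + 0.15×1 + 0.10×4 = 0.90.
- Covariance: 0.35×(-1)(0.3) + 0 + 0.15×(1)(2.3) + 0.10×(2)(2.3) = 0.70.
- r = 0.70 / (√0.90 × 6.206) = 0.12, or about 1.4% of variance.

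*Married and Divorced codes exchanged (1, 3, 2, 4), same data.*

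- Mean code 2.25; variance 1.0875.
- Covariance: 0.35×(-1.25)(0.3) + 0.40×(0.75)(-1.7) + 0.15×(-0.25)(2.3) + 0.10×(1.75)(2.3) = -0.325.
- r = -0.325 / (√1.0875 × 6.206) = -0.05.

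Over all 4! = 24 numberings r runs from -0.25 to +0.25. Eta stays at 0.26 throughout.

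**Illustration 2 (what a test would show).** Assume 100 participants split 40/40/15/5, with samples built to have exactly the stated group means and SD 6. Codes are as listed in the plan.

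| Assumed means | Pearson r (p) | One-way ANOVA |
|---|---|---|
| 20/16/22/24 | 0.10 (p = 0.33) | F = 6.10, p = 0.0008, eta = 0.40 |
| 18/18/22/22 | 0.22 (p = 0.031) | F = 2.37, p = 0.075, eta = 0.26 |

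In the first row the correlation misses a clear difference between groups. Spearman does no better (rho = 0.05, p = 0.63). In the second row the correlation is significant where the overall group comparison is not. The discrepancy can therefore go either way.

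**The case against.** The strongest reply is that the plan does not commit to correlating the codes. One sentence covers two scale scores, two ordered codes and one nominal code, and no single coefficient suits all five. It could be a loose way of saying that associations will be tested, with the bracketed numbers serving as a data-entry key. The indicator coding of the CYP2C19 groups shows that the authors do not always treat a categorical variable as a score. This reply stands in part: a reader might infer that the plan fixes a Pearson correlation on 1 to 4, and the text does not go that far. But nothing in the text says that association was meant, and no group comparison is offered for marital status. The literal reading remains the natural one, and the same edit resolves either reading.

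Three stronger inferences should be resisted:

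- **That the result could have the wrong sign.** A nominal factor has no true sign. The accurate statement is that any sign reported would be an artefact of the numbering.
- **That -0.25 to +0.25 is the uncertainty in this trial.** The plan lists one numbering in advance and nobody will choose among 24. The range shows only that the coefficient depends on labels.
- **That a trial conclusion is at risk.** The analysis is introduced as exploration and has no significance rule of its own. Marital status appears in none of the four hypotheses, is no covariate in any listed model, and plays no part in allocation or in the dose-prediction model.

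Nor does the point extend to the rest of the list. Education is ordered, employment with rising income bands is at least arguably ordered, and the two questionnaire scores are numeric.

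**Conclusion.** The point holds as a minor one, with moderate confidence because the plan's word for the method may have been meant loosely. Taken as written, the planned correlation cannot describe how marital status relates to the three scores, which is the stated purpose. The dependence on labels follows from the variable being nominal and needs no assumption. Its size in this trial is unknown: 0.12 against 0.26 comes from one assumed pattern of shares, means and SD, and other patterns would give a larger or smaller gap.

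**What to change.** Replace the single correlation sentence with a rule by variable type:

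- **Marital status:** a four-level categorical factor, tested with one-way ANOVA (3 degrees of freedom) or Kruskal-Wallis for each of HAM-D, HAM-A and CGI-S, reporting group means with confidence intervals.
- **Education and employment/income:** Spearman rank correlation.
- **Visits:** name the visit or visits analysed. All three scores are measured at V0, V1 and V2, and the sentence does not say which is used.

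The cost is a sentence or two in the SAP. No new data are needed, and the codes can stay as the data-entry key.
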